Primary outcomes include process outcomes. The primary outcome of interest is PrEP uptake. Rates of PrEP uptake will be compared in the first 6 months between those in the intervention and control arms; a sensitivity analysis will be conducted to examine de-identified rates of PrEP uptake among others during the same timeframe. Other process outcomes of interest will investigate the reliability of the strategy to 1) deliver an educational PrEP decision

STU#: STU00217596

guide to women with increased vulnerability to HIV, 2) engage those individuals in the PrEP decision guide, and 3) schedule patients for a dedicated PrEP visit

Secondary outcomes include psychosocial outcomes. In post-pilot interviews, we will obtain the following measures. Differences between intervention and control groups will be explored.

The main secondary outcome is PrEP knowledge measured about 2-6 weeks after randomization to the intervention (receiving the materials) or the control (delayed receipt).

Perceived Risk of HIV. We will use the 8-item Perceived Risk of HIV scale to assess how vulnerable an individual feels to HIV. The scale was developed in the United States and attention was paid to health literacy. Response options vary for each item, though they are measured on a 4-point Likert scale.

PrEP Knowledge. We will use a scale created by our team, drawing from the scale previously created by Welsh for use with men.

PrEP Attitudes. PrEP attitudes will be assessed using a recently developed scale developed that includes 5 items, each measured on a 5-point Likert scale (1=strongly disagree to 5=strongly agree).

[figure not shown]
Health Literacy. We will assess health literacy skills via the Newest Vital Sign (NVS).

Participants will be asked to view a nutrition label and to answer 6 questions about how they would interpret the information. Scores are classified as high likelihood of limited literacy (0-1), possibility of limited literacy (2-3), and adequate literacy (4-6). The NVS has a high correlation with the Test of Functional Health Literacy in Adults and includes both reading and numeracy items.

Health Activation. Patients' engagement in their child's healthcare will be measured using a modified version of our team's 10-item Consumer Health Activation Index (CHAI). Response options are a Likert scale; linear transformation is used to put total scores onto a 0-100 scale, with higher numbers indicating greater activation.

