Participation in this study puts subjects at a minimal risk of discomfort or inconvenience, as they are primarily responsible for providing their own opinions on intervention materials and/or the intervention activities. Participation may make some participants feel uncomfortable, particularly when asked about sensitive topics such as HIV and STIs. Participants will be told they do not need to answer any questions that make them feel uncomfortable. Participation could also result in a loss of privacy, since research and oversight staff may review research findings.

POTENTIAL BENEFITS TO PARTICIPANTS

Participants are not likely to have any direct benefit from being in this research study. However, it is possible that subjects enrolled in the study may indirectly benefit in that they may have, as a result of this study, a better understanding of HIV prevention and PrEP. The results of this study may provide important information regarding how best to increase PrEP uptake among those eligible and interested.

DATA MANAGEMENT AND CONFIDENTIALITY

This is a small pilot study designed to test the feasibility, acceptability, and efficacy of a quality improvement project.

Quantitative Methods. All analyses will be performed using SAS v9.4 (Cary, NC). Descriptive statistics will be first calculated for patient sociodemographic variables, receipt of PrEP (yes/no), variables related to patient satisfaction with the intervention, and process outcomes.

The primary outcomes of interest are PrEP knowledge and PrEP uptake. Rates of PrEP uptake will be compared in the first 6 months between those in the intervention and control arms. Chi-squared tests will be performed with de-identified patient factors, as well as multivariable logistic models, to explore characteristics that may be independently associated with PrEP knowledge and/or receipt of a PrEP prescription. The primary covariate of interest will be the study arm.

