Other process outcomes of interest will investigate the reliability of the strategy to 1) deliver an educational PrEP decision guide to women with increased vulnerability to HIV, 2) engage those individuals in the PrEP decision guide, 3) schedule patients for a dedicated PrEP visit, 4) engage patients prescribed PrEP in a portal post-visit treatment initiation questionnaire, and 5) notify prescribers of their patients' treatment initiation barriers. To achieve this, we will identify the percentage of participants randomized to the EMC2 PrEP strategy who complete each step.

Exploratory bivariate analyses will examine whether there are any systematic, statistically significant differences in PrEP knowledge by study arm and between patients who interacted with the PrEP decision guide and those who did not. Specifically, we will use Pearson chi-squared tests or Fisher exact tests for categorical variables and Student t tests for continuous variables. Statistical significance will be defined as $\alpha < .05$.

Confidentiality

Data collected includes consent forms and information collected during the study interviews (demographics, comprehension testing scores, and feedback on the materials). A master study tracking database via REDCap will contain information linking participants to their study ID numbers. This database is secure and only accessible by study personnel. Each participant will be randomly assigned an identification number to ensure confidentiality of data. The RedCap tracking database designed for this study will be the only place where the ID will appear with the participant's name and contact information (address, email, dob, phone number) in the present study. This database will only be accessible by the research team. Survey data and

STU#: STU00217596

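### PrEP knowledge has no stated scoring or variable type, yet its planned chi-squared and logistic analyses may need a cut-point; a linear model of the score would be better

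*Combined protocol and SAP*

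**What the plan says.** Study Endpoints describes the knowledge instrument in one sentence: "We will use a scale created by our team", drawing on an earlier scale for men. It gives no items, range, direction, scoring rule or threshold. Other variables in the same document do have a stated form. The health literacy test has bands 0-1, 2-3 and 4-6. For health activation, "linear transformation is used to put total scores onto a 0-100 scale". Receipt of PrEP is marked as yes/no in Quantitative Methods.

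Quantitative Methods (under Data Management and Confidentiality) says "The primary outcomes of interest are PrEP knowledge and PrEP uptake". It then names chi-squared tests with patient factors, "as well as multivariable logistic models, to explore characteristics that may be independently associated with PrEP knowledge and/or receipt of a PrEP prescription", and adds: "The primary covariate of interest will be the study arm". No linear or ordinal multivariable model is named anywhere.

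Later in the same section, exploratory bivariate analyses compare knowledge by study arm: "we will use Pearson chi-squared tests or Fisher exact tests for categorical variables and Student t tests for continuous variables". The text does not say which kind of variable knowledge is.

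Study Endpoints, by contrast, calls knowledge the main secondary outcome. Knowledge comes from the post-pilot interviews, 100 per arm (Procedures Involved).

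**The concern.** A binary logistic model, or a chi-squared test on two categories, needs a yes/no outcome. The plan does not say how a scale score becomes one. An analyst following the text would have to choose a threshold, and nothing fixes it before the data are seen.

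Two things are at stake. Splitting a score discards the differences between women on the same side of the cut, so 200 interviews say less about the arm effect. The conclusion can also change with the cut, because two reasonable thresholds may fall on opposite sides of p = 0.05 in the same data.

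**Working it through.** The plan gives no effect size, SD or power figure for knowledge, so there is none to reproduce. What follows is an illustration.

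**Inputs from the document:** 100 interviews per arm; significance level 0.05.

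**Assumptions:** two-sided test; normally distributed score; true difference d = 0.4 SD; covariates explaining a share R² of 0 to 0.3 of the variance.

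**1. Score kept whole.** Power = Φ(d / √(2(1 − R²)/n) − 1.96).
- R² = 0 (the unadjusted t test): 0.4/0.1414 = 2.828; Φ(0.868) = 0.807.
- R² = 0.1: Φ(2.981 − 1.96) = 0.846.
- R² = 0.2: Φ(3.162 − 1.96) = 0.885.
- R² = 0.3: Φ(3.381 − 1.96) = 0.922.

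By formula, adjustment adds 0 to 11.5 points to the t test.

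**2. Score split at the pooled median, unadjusted.** The proportions above the cut are Φ(−0.2) = 0.421 and Φ(0.2) = 0.579, a difference of 0.1585.
- Null standard error: √(2 × 0.25/100) = 0.0707.
- Alternative standard error: 0.0698.
- Power = Φ((0.1585 − 1.96 × 0.0707)/0.0698) = Φ(0.285) = 0.612.

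For 80% power the split needs 155 per arm, against 99 for the score. This agrees with the known efficiency of a median split of a normal score, 2/π = 0.637: 200 × 0.637 ≈ 127 effective interviews.

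**3. Adjusted models by simulation** (arm plus three covariates, 6,000 replicates, d = 0.4):

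| R² | Linear | Median-split logistic | Difference (points) |
|---|---|---|---|
| 0 | 0.784 | 0.611 | 17.3 |
| 0.1 | 0.838 | 0.630 | 20.8 |
| 0.2 | 0.882 | 0.670 | 21.2 |
| 0.3 | 0.912 | 0.701 | 21.1 |

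A repeat run gave 80-93% for linear, 64-70% for split logistic and 79-81% for the t test. Taken together, the loss from splitting is about 16-22 points, and the gain of adjusted linear over the t test is about 0-13 points.

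**4. Dependence on the cut.** At 0.4 SD, cuts at the 40th and 60th percentiles disagree on p < 0.05 in about 24-27% of simulated trials.

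**5. False positives.** With no effect, linear rejects in 4.8-5.3% of trials and the median split in 5.2-5.7%. Any single fixed cut stays near 5%.

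**6. Short or bounded scales.** These were sums of 5, 10 or 15 yes/no items, with 1-58% of controls at the maximum and a difference of about 0.4 SD.
- Linear: 85-90% power.
- Linear with robust (HC3) standard errors: 84-89%.
- Near-median split: 65-76%.
- Proportional-odds model (5 and 10 items): 84-89%.

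**The case against.** The strongest reply is that a continuous comparison may already be planned. If knowledge is treated as continuous, the bivariate paragraph gives a Student t test by arm. Under randomisation that is a valid comparison and needs no cut-point. This stands in part, and it limits the gain to about 0-13 points. It does not settle the matter, because that analysis is labelled exploratory, is unadjusted, and depends on a variable type that the plan never states.

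Second, chi-squared plus logistic is a coherent plan for a categorical outcome, and logistic need not mean binary. If an ordinal model was meant, the loss largely disappears. That also stands, but the plan does not say so.

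Third, a scoring rule may exist in the source instrument. The gap is that this document does not state it; it does not follow that no rule exists.

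Fourth, this is a pilot without a power claim. A reader might infer that the trial misses a power target, but there is no target to miss.

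A reader might also infer that the type I error is inflated. The document does not support that. A fixed cut keeps about 5%, and inflation (about 9% for the better of two cuts, 15-16% for the best of five) needs a search over cuts that the plan does not propose.

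**Conclusion.** The point holds in a conditional form. The firm defect is that the scoring and variable type of knowledge are unstated, while the analyses named for it alongside the prescription outcome are ones that may require categories. If the score is split, the cost is about 16-22 points of power against adjusted linear regression at 0.4 SD, plus a result that varies with the cut. If the t test is used, the gain from the change is modest. These sizes rest on an assumed effect, score shape and covariate strength, none of which the document gives.

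It would go too far to say that the plan forces dichotomisation or leaves knowledge with no valid arm comparison. Nor should the importance rest on knowledge being a primary outcome, since the document gives it two different ranks. This is a cheap improvement.

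**What to change.** 1. In Study Endpoints, state the items, range, direction and scoring rule of the knowledge scale, and that it is analysed as a score.
2. For knowledge, replace both the chi-squared tests and the logistic model with one main analysis: linear regression of the score on study arm plus a short list of demographics, named before the data are seen. Use robust standard errors throughout, and report the adjusted mean difference with its 95% CI.
3. Report the Student t test as the unadjusted result. It estimates the same kind of mean difference, so the two results are on one scale.
4. Make two sensitivity analyses: the main model with health literacy (NVS) added, kept out of the main model because it is measured after randomisation; and a proportional-odds model.
5. Keep chi-squared and logistic methods for the yes/no prescription outcome.
6. Label any binary knowledge analysis supportive, with its threshold fixed and justified in advance.
7. Reconcile the rank of knowledge: main secondary in Study Endpoints, primary in Quantitative Methods.

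The cost is a few sentences and no new data, since demographics and health literacy are already collected at the interview. The downside is small: a ceiling makes a mean difference less natural to interpret, which the ordinal check covers. A ceiling is possible because the last 50 intervention interviewees see the materials just before the questions. The choice of model does not address that feature of the design.

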Several studies have also noted that primary care providers are well positioned to prescribe PrEP to women who are already engaged in the health system. Women themselves have noted a preference for primary care providers to normalize PrEP conversations and perform regular screening for potential PrEP uptake; this is particularly the case among women who have increased vulnerability to HIV. Yet, while primary care represents the healthcare frontlines for the vast majority of adult women, primary care providers are not always adequately prepared to counsel on, or deliver PrEP.

With the near universal adoption of EHRs across the United States, opportunities now exist to increase patient-provider discussion and monitoring of PrEP in primary care with minimal disruption to clinical workflow or timing. EHR alerts have already been used effectively to increase HIV testing in primary care, and efforts are underway to use artificial intelligence within the EHR to predict potentially eligible PrEP users – a technique that relies on existing, yet limited, laboratory data and structured EHR fields. However, no comprehensive EHR-based interventions have been developed to use EHR data for “case-finding” potentially eligible patients, while also facilitating informed decision-making for HIV prevention and supporting PrEP uptake within primary care.

STU#: STU00217596

Our team recently developed and evaluated the Electronic health record Medication Complete Communication (**EMC²**) strategy to 'hardwire' provider/patient communication & surveillance of select prescription (Rx) medications. EMC² uses widely available technologies to promote:

- **provider counseling** at the point of care, prompted via EHR 'best practice' alerts (BPAs) linked to the signing of a medication order or a specified diagnosis
- **dissemination of understandable, actionable Rx instructions and risk information** automatically via the EHR or patient portal
- **routine community-based surveillance of Rx use** either by interactive voice response (IVR), text messaging, or EHR patient-portal platforms, to assess patient Rx experiences and notify clinicians of any problems via EHR secured message

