Acceptability of the Strategy. Using 5-point Likert scale response options (1=very unsatisfied to 5=very satisfied), intervention participants will be asked to rate their satisfaction with various strategy components, including the materials, the dedicated PrEP visit, and the clinic follow-up activities.

Demographic Characteristics. We will collect a range of sociodemographic characteristics on the patient. This includes, but is not limited to: age, race/ethnicity, marital status, household income, and insurance status.

STUDY INTERVENTION(S) / INVESTIGATIONAL AGENT(S):

The Figure below provides an overview of key intervention activities.

Briefly, EMC² PrEP will help: 1) identify female patients in primary care who are at increased vulnerability to HIV due to prior suspected or confirmed bacterial STIs; 2) identified patients will receive an interactive, and educational PrEP decision guide via the patient EHR portal (they may also receive up to 3 reminders via the EHR portal to view the decision guide); 3) those who are interested in learning more about PrEP will be directed to schedule a dedicated visit with a dedicated PrEP provider; 4) during which PrEP options will be discussed and prescribed as appropriate.

STU#: STU00217596

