Our pilot study will be conducted at select Northwestern Medicine (NM) primary care, after receiving committee approval to inform potentially eligible women about PrEP by providing them with an educational material that will educate them on PrEP and provide decision support for those who might be interested in speaking with a dedicated PrEP provider about PrEP use. We will not be altering the standard of care; rather, we will be providing additional materials and support to those who may benefit. A recent EHR data pull indicates there are ~1400 female patients who are potentially eligible for PrEP in primary care. For evaluation purposes, these women will be 1:1 randomized to either: 1) immediate receipt of the EMC² PrEP strategy as part of the intervention group or 2) a delayed receipt of the EMC² PrEP educational materials as part of the control group. Immediate receipt may take place over a rolling period over the course of several months. This not only ensures everyone receives the strategy, but it also allows for a practical rollout that respects the clinic bandwidth. Randomization will occur using a random number generator. EHR data will be evaluated in aggregate to determine, for example, how many women received the PrEP decision guide, opened it, interacted with it, scheduled a dedicated PrEP visit and/or received a PrEP prescription. Data will also be evaluated during the acute period to compare those who immediately received the EMC² PrEP strategy, and those who were delayed in their receipt of the strategy.

PROCEDURES INVOLVED:

Study Design Overview

To achieve our objectives, mixed-methods research will be conducted to adapt, pilot, and disseminate the EMC² strategy for use in PrEP decision making among women in primary care.

Aim 1: Adaptation Phase

During the Adaptation Phase (Aim 1), we will: 1) obtain clinician and EHR analyst input from various committee approval meetings; 2) develop and refine the content of the PrEP decision guide via cognitive interviews with the target audience (N=15), and 3) construct the technological build for both the decision guide and the post-visit treatment initiation questionnaire. A Scientific Advisory Board (N=3) will provide guidance on the strategy and intervention content throughout this process.

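### A single whole-arm denominator makes process steps 4 and 5 (post-visit questionnaire, prescriber notification) measures of reach rather than reliability, and the protocol's lists of steps do not agree

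*Combined protocol and SAP*

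**What the plan says.** Quantitative Methods, under DATA MANAGEMENT AND CONFIDENTIALITY, lists five process outcomes framed as the reliability of the strategy. Steps 1 to 3 cover delivery of the decision guide, engagement with it and scheduling of a PrEP visit. Step 4 is to "engage patients prescribed PrEP in a portal post-visit treatment initiation questionnaire". Step 5 is to "notify prescribers of their patients' treatment initiation barriers". One rule then covers all five: "we will identify the percentage of participants randomized to the EMC2 PrEP strategy who complete each step". No other denominator is given. PROCEDURES INVOLVED, Aim 2, puts the intervention arm at 700 of about 1400 women randomized 1:1.

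Other sections describe the steps differently:

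- STUDY ENDPOINTS gives the same list but ends it at the third item: "engage those individuals in the PrEP decision guide, and 3) schedule patients for a dedicated PrEP visit".
- STUDY INTERVENTION(S) ends its prose summary at the visit, "during which PrEP options will be discussed and prescribed as appropriate". Its examples of EHR data to be evaluated end at "scheduled a dedicated PrEP visit and/or received a PrEP prescription".
- PROCEDURES INVOLVED, Aim 1, plans to "construct the technological build for both the decision guide and the post-visit treatment initiation questionnaire".
- Apart from step 5, clinician notification appears only in BACKGROUND, as part of the general EMC² approach: "to assess patient Rx experiences and notify clinicians of any problems via EHR secured message".

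**The concern.** A reliability measure should show how often a step happens when it is supposed to happen. Step 4 is limited by its own wording to women prescribed PrEP. Step 5 needs a prescribed patient with a barrier, and a notification is not something that a participant completes. Dividing either count by the whole arm mixes two things: how many women reached the point where the step applies, and how well the step then worked.

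Feasibility is one of the Aim 2 objectives, and Aim 3 is to write an operating protocol for dissemination. A team deciding whether to carry the questionnaire and the notice forward needs the second quantity, and the stated rule does not give it. The differing lists add a prior question: are these two steps part of the piloted strategy at all?

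**Working it through.** **Inputs.** About 1400 women, 1:1 allocation and 700 in the intervention arm come from PROCEDURES INVOLVED, Aim 2. The denominator rule and the wording of steps 4 and 5 come from Quantitative Methods. The documents give no expected prescription rate, questionnaire completion rate or barrier rate, so all rates below are assumptions.

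**Arm size.** 1400 × 1/2 = 700, which reproduces the stated figure.

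**Ceiling.** Let m be the number of women in the arm prescribed PrEP and x the number who complete the questionnaire. Then x ≤ m, so x/700 ≤ m/700, which is the arm's prescription rate. If notifications arise from questionnaires that report a barrier, their number is at most x, so step 5 has the same ceiling or a lower one.

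**Numbers.** The table takes about 80% completion among women prescribed PrEP, rounded to whole women. Intervals are exact (Clopper-Pearson).

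| Assumed prescription rate | m = 700 × rate (ceiling for step 4) | x | Plan's figure, x/700 | Conditional figure, x/m (95% CI) |
|---|---|---|---|---|
| 1% | 7 | 6 | 0.9% | 86% (42 to 100) |
| 2% | 14 | 11 | 1.6% | 79% (49 to 95) |
| 5% | 35 | 28 | 4.0% | 80% (63 to 92) |
| 10% | 70 | 56 | 8.0% | 80% (69 to 89) |

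Completion among the women concerned is about the same in every row, yet the plan's figure rises about ninefold (8.0/0.86 ≈ 9.3) because the prescription rate changes.

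**Same figure, different reliability.** The result 7/700 = 1.0% arises if 7 women are prescribed PrEP and all complete the questionnaire (7/7 = 100%, 95% CI 59 to 100). It also arises if 14 are prescribed PrEP and half complete it (7/14 = 50%, 95% CI 23 to 77). The whole-arm percentage cannot tell these apart.

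**Which conditional denominator.** The preceding item on the list will not serve. Step 3 is scheduling a visit, and a woman may schedule without being prescribed PrEP; the EHR data examples, with their and/or, also allow a prescription without a scheduled visit. For step 5, completed questionnaires would include those with no barrier to report. The populations that fit the wording are women prescribed PrEP (step 4) and completed questionnaires that report a barrier (step 5).

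**Lists side by side.** Quantitative Methods has five steps and STUDY ENDPOINTS has three. The prose of STUDY INTERVENTION(S) ends at prescribing. Aim 1 procedures include building the questionnaire. The figure in STUDY INTERVENTION(S) is not available for checking, so the firmly established mismatch is between STUDY ENDPOINTS and Quantitative Methods.

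**The case against.** The strongest reply is that a percentage of the whole arm at each step is a legitimate cascade. Later steps are always bounded by earlier ones, step 3 included. Step 4 names its own population, and counts of prescriptions are planned anyway, so a reader could work out the conditional figure. Much of this stands: the whole-arm figure is valid as a measure of reach and should stay. What does not stand is its use as the only measure where the stated aim is reliability. Leaving the reader to derive the other figure also gives no interval and leaves step 5 undefined.

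Four stronger readings are tempting, and the documents do not support them:

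- That the denominator is all randomized women, about 1400. The rule names those randomized to the strategy, about 700.
- That the questionnaire is missing from the protocol. Its build is an Aim 1 procedure, the intervention prose is offered as a brief summary, and the satisfaction measure mentions clinic follow-up, which may or may not refer to it.
- That a questionnaire that works would be declared a failure, or that a dropped step would be reported as 0%. There is no success threshold, and nothing says that a dropped component would be reported.
- That a primary endpoint is compromised. STUDY ENDPOINTS does class process outcomes as primary, but it singles out PrEP uptake and does not list steps 4 and 5. Quantitative Methods names knowledge and uptake as primary and places these five among other process outcomes.

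**Conclusion.** The point holds within limits. For steps 4 and 5 the stated rule gives reach, bounded by the arm's prescription rate, while the declared aim is reliability. At an assumed 2% prescription rate and about 80% completion, the plan would report 1.6% (11/700) where the figure for whether the step works is 79% (11/14). The gap narrows as the prescription rate rises, but even at an assumed 10% it is 8.0% against 80%. The ceiling itself needs no assumption beyond the wording of the two steps; for step 5 the calculation also takes notifications to arise from the questionnaire, which the documents do not spell out.

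The process lists in STUDY ENDPOINTS and Quantitative Methods disagree and must be reconciled. The consequence is limited, because these outcomes are descriptive and carry no hypothesis test, power calculation or decision threshold.

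**What to change.** 1. Keep the percentage of the whole intervention arm for each step, labelled as reach.
2. For steps 4 and 5 add a conditional percentage with an exact 95% interval, as the reliability measure. For step 4, use questionnaires completed among intervention-arm women prescribed PrEP. For step 5, use prescriber notifications sent among completed questionnaires that report a barrier. Show numerators and denominators.
3. State once whether steps 4 and 5 belong to the piloted strategy, and make STUDY ENDPOINTS, STUDY INTERVENTION(S) and Quantitative Methods list the same steps.

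The cost is a sentence on denominators, an extra table column and a consistency edit. The counts are ones that the plan already needs if it reports these steps. The drawback is precision: the conditional figures may rest on very few women, with intervals as wide as 42 to 100 for 6 of 7. They should be read as descriptive.
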